### 217 **Primary Outcome:**

218 Clinical Global Impression of Improvement Scale (CGI-I). The response rate is 219 defined as the number of participants self-reporting minimal change or larger on 220 the Clinical Global Impression of Improvement Scale (CGI-I) scale, divided by 221 the number of participants in each group. The CGI-Improvement is a self-222 reported scale of improvement ranging from 1 to 7 (1 is Very Much Improved, 7 223 is Very Much Worsened) and will be measured after completing 8 weeks of the 224 fixed, highest-tolerable dose. Each rating is well defined to maximize accuracy. 225 Participants reporting 3 as Minimally Improved, 2 as Much Improved, or 1 as Very 226 Much Improved in the CGI-I will be deemed responders to treatment, and the 227 number of responders to non-responders will be compared between the two arms -228 CGI-Severity (CGI-S) and CGI-Improvement (CGI-I).

229	
230	
231	Secondary Outcomes:
232	1. CGI-Severity. The CGI-Severity scale ranges from 1 to 7, where 1 is normal
233	function and 7 is complete anosmia. This assessment will provide subjective data
234	on patients' baseline olfactory function prior to beginning the trial, after 8-week
235	Fixed-Dose period, and 4 weeks after completion of Taper-Down phase.
236	2. CGI-Improvement. The CGI Improvement will also be administered 4 weeks
237	after completion of Taper-Down phase which same analysis as described above.
238	3. University of Pennsylvania Smell Identification Test (UPSIT).  The UPSIT is
239	composed of 40 strips of microencapsulated odorants, which are present on the
240	bottom of each page, just below a four-alternative multiple-choice question. For a
241	given item, the patient releases an odor by scratching the microencapsulated pad
242	with a pencil tip, smells the pad, and indicates the odor quality from four
243	alternatives. Even if no smell is perceived, a response is required (i.e., the test is
244	forced-choice). The subject's total correct score out of the 40 items is
245	determined. 
246	The total UPSIT score can range from 0 to 40 and scores are interpreted as the
247	level of absolute smell function (i.e., normosmia, mild hyposmia, moderate
248	hyposmia, severe hyposmia, and anosmia), using the age- and sex-related
249	normative classification system described in the UPSIT manual (Table 1) The
250	minimal clinically important difference in UPSIT score is 4.

Disease Classification Based on UPSIT		Women	Men

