### 301 D3 Dose Rationale and Risk/Benefits

Gabapentin dosing for this study mirrors dosing for the prior study "Relief of Idiopathic
 Subjective Tinnitus" (IRB #02-0717)

- Following randomization, participants in the gabapentin arm will take gradually titrated dosages in order to achieve a dose of 3600mg/d or highest tolerable dose. The titration schedule will span a maximum 4 weeks to reach 3600mg/d.
- 307 Week 1, 900 mg/d
- 308 Week 2, 1800 mg/d
- 309 Week 3, 2700 mg/d
- 310 Week 4, 3600 mg/d
- 311

312	Gabapentin (300 mg per capsule) and placebo will be supplied to patients in
313	identical opaque capsules in blinded fashion. The medications will be distributed in 4
314	separate vials representing each of the four weeks of the Titration Period. All
315	participants will be provided an equal number of capsules and instructed to follow a TID
316	(i.e., 3 times per day) dosing schedule. All participants' dosages will be titrated to a
317	maximum dose of 3600 mg/d, regardless of any possible beneficial effect achieved at
318	lower dosages. If intolerable adverse reactions occur, the dosage will be decreased to
319	previous tolerable dose (e.g. if 2700mg/d is intolerable, dosage will be decreased to 1800
320	mg/d). If, during the first week, 900 mg/d is intolerable, dosing will be decreased by 300
321	mg/d per day until tolerable (i.e., 600 mg/d, 300mg/d) or until they are no longer taking
322	the medication. The dose established during the Titration Period will be maintained
323	throughout the Fixed-Dose period. Participants receiving the matching placebo capsules
324	will be provided similar instructions for titration and de-escalation, should side effects
325	develop.
326	-

The potential benefit to the participant is improvement of their olfactory dysfunction
using this therapy. The potential benefit to the society is the use of the pilot study results
to initiate a larger trial to further evaluate the efficacy of gabapentin in the treatment of
post-COVID-19 olfactory dysfunction.

331

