### 341 E1 Overview or Design Summary

This study will be a double-blinded, placebo-controlled, randomized pilot clinical trial to evaluate the efficacy of gabapentin to improve post-COVID-19 olfactory dysfunction.

- 344 This study will also describe adverse effects related to oral gabapentin use.
- 345

This study will be conducted via virtual research guidelines and procedures. We will not require in-person patient participation or evaluation. Following initial evaluation to ensure potential participants meet all inclusion criteria and none of the exclusion criteria,

the research study will be explained in full via Zoom call, phone call if necessary.

350 Participants will then be randomized in a 1:1 allocation via permuted-block sequencing

into the oral gabapentin group or the placebo group. All assessments will be conductedthrough a HIPAA-compliant online survey form. Baseline assessments will help us

determine subjective and objective rates of olfactory dysfunction. Assessments will be

354 conducted again after the 8-week Fixed-Dose period and 4 weeks after completing taper.

355 356	The primary objective of this study is to assess the efficacy of oral gabapentin in improving olfactory dysfunction secondary to COVID-19.
357	E2 Subject Selection and Withdrawal
358	
359	2.a Inclusion Criteria
360	Participants will be recruited based on the following inclusion criteria:
361	- Men and women between the ages of 18 and 65 years
362	- Residing within the states of Missouri or Illinois
363	- Clinically diagnosed or subjective olfactory dysfunction (anosmia, hyposmia,
364	or parosmia) of at least 3 months duration associated with COVID-19
365	infection

- 366- initial UPSIT score consistent with diminished olfactory function (score  $\geq 6$ 367and  $\leq 33$  in men and score  $\geq 6$  and  $\leq 34$  in women).
- Willing to respond daily to study surveys, preferably through smartphone with
   unlimited texting plan.
- In possession of all 7 household items associated with *NASAL-7*: soap, burnt
  candle, peanut butter, herb, garlic, lemon, and coffee

373 2.a Exclusion Criteria

Individuals will not be allowed to participate in this study if they meet one or more of thefollowing exclusion criteria:

- Clinically diagnosed olfactory dysfunction secondary to non-COVID-19 viral
   infection, genetic abnormalities or congenital dysfunction, trauma, nasal
   polyps, neurodegenerative disorders
- 379
  380

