### 542 Gabapentin Study Flow Chart

549	
550	
551	
552	
553	
554	a. Federal guidelines require timely reporting (within 15 calendar days) of an
555	unanticipated or life-threatening event or death occurring within 30 days of
556	active study participation.
557	
558	
559	Titration Period: maximum duration 4 weeks
560	
561	Placebo. In this study, we plan to use an inert placebo and not an active drug
562	or non-active drug with side effects similar to gabapentin. Participants randomized to the
563	Placebo arm will participate in a 4-week Titration Period. Placebo will be supplied to
564	patients in opaque capsules in blinded fashion. The medications will be distributed in 4
565	separate vials representing each of the four weeks of the Titration Period. If intolerable
566	adverse reactions occur, the dosage will be decreased to prior tolerable dose.
567	Gabapentin. Participants randomized to the gabapentin arm will take
568	gradually titrated dosages of gabapentin as follows:
569	
570	Week 1, 900 mg/d (300 mg TID)
571	Week 2, 1800 mg/d (600 mg TID)
572	Week 3, 2700 mg/d (900 mg TID)
573	Week 4, 3600 mg/d (1200 mg TID)
574	
575	Gabapentin (300 mg per capsule) will be supplied to participants in opaque
576	capsules in blinded fashion identical to the supply of Placebo. The medications will be
577	distributed in 4 separate vials representing each of the four weeks of the Titration Period.
578	All participants' dosages will be titrated to a maximum dose of 3600 mg/d, regardless of
579	any effect achieved at lower dosages. If intolerable effects occur, dosage will be
580	decreased by 1 dose (300 mg) step (e. g. if 2700 mg/d is intolerable, dosage will be
581	decreased to 2400 mg/d). Further de-escalation will be determined by PI clinical
582	judgement to prior tolerable dose. Participants with intolerable effects may have a lower
583	maximum dose than 3600mg/d and may complete the Titration Period in less than 4
584	weeks. The dose established during the Titration Period will be maintained throughout
585	the Fixed-Dose period.

WEEK 1	WEEK 2	WEEK 3	WEEK 4
900 MG	1800 MG	2700 MG	3600 MG
1 MORNING 1 NOON 1 NIGHT (21 PILLS)	2 MORNING 2 NOON 2 NIGHT (42 PILLS)	3 MORNING 3 NOON 3 NIGHT (63 PILLS)	4 MORNING 4 NOON 4 NIGHT (84 PILLS)

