### 587 Gabapentin (300 mg pill) Titration Schedule

588

586

589 If at any point during the Titration Period, the participant wishes to discontinue 590 the medication for any reason, they will be instructed to follow the taper down schedule 591 (see below) in order to safely stop the medication. The participant will be informed that 592 any abrupt stoppage of gabapentin could cause serious adverse effects.

Participants will be contacted by telephone or video call by the Research Assistant
(RA) at the end of Titration period. The purpose of this call will be to query the
participants about adverse effects. Participants will be provided with a paper calendar
and asked to maintain diaries of olfactory and taste symptoms and adverse effects
possibly related to the intervention.

598 Participants will not complete any forms at the completion of Titration period.599 Instead, they will proceed directly to Fixed-Dose Period.

### 600 601

Fixed-Dose Period: duration 8 weeks

602During the Fixed-Dose period, participant's dose will remain at their maximum tolerated603dosage established during the Titration phase. The study drug will be distributed in eight604separate vials representing the eight weeks of the Fixed-Dose period. The RA will605contact the participants at the end of Week 4 to administer the blind assessment using606REDCap (survey titled: "Blind Assessment"). Participants will complete the following607forms after completing the Fixed-Dose Period (survey titled: "FixedDoseSurvey"):

- 608
- 609 1.) Clinical Global Impression of Severity Scale (CGI-S).

610 2.) Clinical Global Impression of Improvement Scale (CGI-I)

- 611 3.) University of Pennsylvania Smell Identification Test (UPSIT)
- 612 4.) Olfactory Dysfunction Outcomes Rating (ODOR)
- 613 5.) *NASAL-7*
- 6.) *Clinical Global Impression-Severity Scale for Parosmics (CGI-P)*
- 615 7.) Adverse Event assessment
- 616 8.) Compliance
- 617

618 *Adverse events*. Any unintentional or unfavorable clinical sign or symptom, any new

619 illness or disease or the deterioration of existing disease or illness, or any clinically

620 significant deterioration in any laboratory assessments or clinical tests while participating

621 in this study will be captured. The study coordinator will contact participants virtually to

622 answer questions and assess adverse effects after Titration period, Fixed-Dose period,

- 623 and 4 weeks after Taper.
- 624

- 625 Taper Down: maximum duration 2 weeks

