- 626 Upon completion of the Fixed-Dose period, all participants in the study will be
- 627 titrated off study drug through a taper down period of maximum 2 weeks. Taper schedule
- 628 will directly relate to maximum gabapentin dose achieved during trial and is described in
- the Table below. The study drug will be distributed in 2 separate vials representing eachof the two weeks of the Taper-Down Period. It should be noted, participants randomized
- to placebo will also receive sufficient capsules to complete a taper down. In this way, the
- 632 blind will be maintained.

AT 3600 MG	AT 2700 MG	AT 1800 MG	AT 900 MG
FOR 3 DAYS 3 MORNING 3 NOON 3 NIGHT	FOR 3 DAYS 2 MORNING 2 NOON 2 NIGHT	FOR 3 DAYS 1 MORNING 1 NOON 1 NIGHT THEN STOP	NO TAPER REQUIRED
NEXT 3 DAYS 2 MORNING 2 NOON 2 NIGHT	NEXT 3 DAYS 1 MORNING 1 NOON 1 NIGHT THEN STOP		
FINAL 3 DAYS 1 MORNING 1 NOON 1 NIGHT THEN STOP			

634 Gabapentin Taper Down Schedule

635

635	
636	End of Study Intervention: Exit Interview/ Data Collection: 4 weeks after
637	completing Taper Down
638	The RA will contact the participants to query participants about compliance
639	with taper-down schedule and maintenance of diaries. Participants will complete the
640	following forms (survey titled: "FinalSurvey"):
641	1. Clinical Global Impression of Severity Scale (CGI-S).
642	2. Clinical Global Impression of Improvement Scale (CGI-I)
643	3. University of Pennsylvania Smell Identification Test (UPSIT)
644	4. Olfactory Dysfunction Outcomes Rating (ODOR)
645	5. NASAL-7
646	6. Clinical Global Impression-Severity Scale for Parosmics (CGI-P)
647	
(10	
648	F3 Safety and Adverse Events
649	
650	3.a Safety and Compliance Monitoring
	v I O

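### The primary CGI-I is timed from the end of the Fixed-Dose period, so participants who finish titration early are rated earlier, and this may happen more often on gabapentin

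*Combined protocol and SAP*

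**What the plan says.** **Timing of the ratings.** Section C3 says the primary CGI-I "will be measured after completing 8 weeks of the" fixed dose. Section E1 says assessments are "conducted again after the 8-week Fixed-Dose period and 4 weeks after completing taper". Section F2 heads the last visit "End of Study Intervention: Exit Interview/ Data Collection: 4 weeks after" the taper. The text ties none of these to a week counted from randomization or first dose.

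**Length of titration.** The F2 heading above both arms reads "Titration Period: maximum duration 4 weeks". The gabapentin paragraph adds that participants with intolerable effects may end up below the "maximum dose than 3600mg/d and may complete the Titration Period in less than 4" weeks. When titration ends, "they will proceed directly to Fixed-Dose Period".

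**Placebo.** The F2 placebo paragraph says those in the "Placebo arm will participate in a 4-week Titration Period". Section D3 says placebo participants "will be provided similar instructions for titration and de-escalation, should side effects" arise. Section F3 (Safety and Compliance Monitoring) gives titration of at most 4 weeks for everyone. The placebo is inert by choice (F2).

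**Taper.** The F2 taper table gives 9, 6, 3 or 0 days for 3600, 2700, 1800 or 900 mg/d.

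**Analysis.** Section G3 compares crude responder rates with Fisher's exact test. The UPSIT mixed model has group and time as fixed factors. Neither is said to use the actual day of rating.

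**The concern.** The CGI-I asks how much a participant has improved since baseline, in a condition that sections B1 and B2 say can take months to recover. The answer can therefore depend on how long the participant has been followed. Here that length depends on tolerability, which arises after randomization and can itself be affected by treatment. Randomization does not balance it.

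If more gabapentin participants stop titrating early, their arm is rated sooner on average and part of the natural recovery is missed. The likely direction is against gabapentin. The responder rate at the end of the Fixed-Dose period is exposed first, and the UPSIT change at that visit in the same way. Because the pilot is meant to lead to a larger trial (D3), the same schedule could be carried forward.

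**Working it through.** **The plan's own figure.** G1 gives 30% response on placebo, a 25-point target (so 55% on gabapentin) and 20 evaluable per group. The Wald interval is 0.25 ± 1.96 × √(0.30×0.70/20 + 0.55×0.45/20) = 0.25 ± 1.96 × 0.151, or −4.6% to 54.6%. This agrees with the stated −5% to 55%, a half-width of about 30 points.

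**Timing.** Let T be titration length in weeks. The primary rating falls at week T + 8 from first dose, and the final visit at week T + 8 + (taper days)/7 + 4. The documents do not say exactly when a shortened titration ends; I assume after the last full week tolerated.

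| Dose reached | T | Taper days | Primary week | Final week |
|---|---|---|---|---|
| 3600 mg/d | 4 | 9 | 12 | 17.3 |
| 2700 mg/d | 3 | 6 | 11 | 15.9 |
| 1800 mg/d | 2 | 3 | 10 | 14.4 |
| 900 mg/d | 1 | 0 | 9 | 13.0 |

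The spread is 3 weeks at the primary rating and 4.3 weeks at the final visit. If everyone titrated for 4 weeks, the primary spread would be zero, but the final visit would still run from week 16.0 to 17.3 because of the taper.

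**Effect on the difference.** The documents give no intolerance rate and no recovery curve, so both are assumed. Take response to accrue at a constant hazard up to the G1 rates at week 12: rate(w) = 1 − (1 − p)^(w/12).

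| Rating week | p = 30% | Loss | p = 55% | Loss |
|---|---|---|---|---|
| 11 | 27.9% | 2.1 | 51.9% | 3.1 |
| 10 | 25.7% | 4.3 | 48.6% | 6.4 |
| 9 | 23.5% | 6.5 | 45.1% | 9.9 |

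Let g and c be the shares finishing early on gabapentin and placebo.

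- Only natural recovery is lost: bias = (g − c) × loss at 30%.
- Drug response also accrues with time: bias = g × loss at 55% − c × loss at 30%.

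| g vs c | Weeks early | Natural recovery only | Drug response too |
|---|---|---|---|
| 20% vs 5% | 1 | 0.3 | 0.5 |
| 20% vs 5% | 3 | 1.0 | 1.7 |
| 40% vs 10% | 1 | 0.6 | 1.0 |
| 40% vs 10% | 3 | 2.0 | 3.3 |

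For example, 0.15 × 2.1 = 0.3 and 0.40 × 9.94 − 0.10 × 6.53 = 3.3. Linear accrual of natural recovery (30/12 = 2.5 points per week) gives 0.4 to 2.3. With equal early shares, the natural-recovery bias is zero.

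**The case against.** **Phase-anchored timing is a legitimate choice.** It gives every completer the same 8 weeks at a stable dose, and the same 4 weeks since taper at the final visit. This stands in part. Moving only the survey dates would create a new mismatch. With 1 week of titration the Fixed-Dose period ends at week 9, so a week-12 rating would come 3 weeks after it. Visit timing and phase length therefore have to be settled together.

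**Placebo is not clearly fixed at 4 weeks.** A reader of the placebo paragraph might infer an arm-specific rule. The documents do not support that. It is one sentence against the heading above it, D3 and F3. Only the research pharmacist is to know assignments (E3, Blinding of Study Drug), so blinded staff could not apply such a rule. What remains is a contradiction to reconcile.

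**The arm difference is conditional.** Finishing early is optional, no intolerance rate is given, and the flow chart could not be read in the text available. A reader might take it as established that the arms are rated at different times; the text shows only that they may be.

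**The size is uncertain.** A reader might put the loss as high as 5 points (50% × 9.9). That needs half the gabapentin arm to be rated 3 weeks early and no placebo participant to be. The 30% comes from a study of another treatment, with its duration not stated in G1, and need not be all natural recovery. Entry requires at least 3 months of dysfunction, so fast recoverers are largely excluded. B1 also describes smell that returns and is then distorted, which constant-hazard accrual does not allow. These points limit how far the figures can be trusted, but do not remove the dependence of rating time on tolerability.

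**Conclusion.** The point holds in conditional form. The primary rating is tied to the end of a drug phase whose start depends on tolerability, and the analysis ignores elapsed time. With an inert placebo, gabapentin participants may be rated somewhat earlier on average. The illustrative loss is about 0.3 to 3.3 of the targeted 25 points, against gabapentin. It rests on the assumed early-finish shares (20–40% against 5–10%), on shortening by 1–3 weeks, and on response accruing steadily to week 12.

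This is a modest bias beside a 30-point half-width and would not by itself decide how the pilot is read. It is still worth removing, because it is systematic and cheap to correct before a larger trial.

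**What to change.** 1. **Phase length.** Reconcile D3, F2 and F3 into one stated rule that applies to both arms. What that rule is, and how the dose periods are filled, is for the sponsor to decide.
2. **Primary rating.** Set it at the same study week from first dose in both arms; week 12 is already the planned maximum. Settle this together with item 1, so that nobody is rated after their Fixed-Dose period has ended.
3. **Recording and reporting.** Record the actual day of each rating. Report time from first dose to rating by arm for the primary and final visits, with a sensitivity analysis that takes account of it.
4. **Final visit.** Report its timing, but do not require week 18. Even with the Fixed-Dose period ending at week 12 for all, a week-18 visit would fall 18 − 12 = 6 weeks off drug with no taper, against 18 − 12 − 9/7 = 4.7 weeks after a 9-day taper.

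**Cost.** Protocol wording, survey timing and one extra analysis. Some early finishers are rated up to 3 weeks later, within the 18 weeks of availability already required at entry (E2). Vials for 4 titration weeks and 8 fixed-dose weeks are already planned (E3, F2), though the sponsor would need to check that supply fits the rule chosen. The planned sample size and the stated interval do not change.

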### 587 Gabapentin (300 mg pill) Titration Schedule

588

586

589 If at any point during the Titration Period, the participant wishes to discontinue 590 the medication for any reason, they will be instructed to follow the taper down schedule 591 (see below) in order to safely stop the medication. The participant will be informed that 592 any abrupt stoppage of gabapentin could cause serious adverse effects.

Participants will be contacted by telephone or video call by the Research Assistant
(RA) at the end of Titration period. The purpose of this call will be to query the
participants about adverse effects. Participants will be provided with a paper calendar
and asked to maintain diaries of olfactory and taste symptoms and adverse effects
possibly related to the intervention.

598 Participants will not complete any forms at the completion of Titration period.599 Instead, they will proceed directly to Fixed-Dose Period.

### 600 601

Fixed-Dose Period: duration 8 weeks

602During the Fixed-Dose period, participant's dose will remain at their maximum tolerated603dosage established during the Titration phase. The study drug will be distributed in eight604separate vials representing the eight weeks of the Fixed-Dose period. The RA will605contact the participants at the end of Week 4 to administer the blind assessment using606REDCap (survey titled: "Blind Assessment"). Participants will complete the following607forms after completing the Fixed-Dose Period (survey titled: "FixedDoseSurvey"):

- 608
- 609 1.) Clinical Global Impression of Severity Scale (CGI-S).

610 2.) Clinical Global Impression of Improvement Scale (CGI-I)

- 611 3.) University of Pennsylvania Smell Identification Test (UPSIT)
- 612 4.) Olfactory Dysfunction Outcomes Rating (ODOR)
- 613 5.) *NASAL-7*
- 6.) *Clinical Global Impression-Severity Scale for Parosmics (CGI-P)*
- 615 7.) Adverse Event assessment
- 616 8.) Compliance
- 617

618 *Adverse events*. Any unintentional or unfavorable clinical sign or symptom, any new

619 illness or disease or the deterioration of existing disease or illness, or any clinically

620 significant deterioration in any laboratory assessments or clinical tests while participating

621 in this study will be captured. The study coordinator will contact participants virtually to

622 answer questions and assess adverse effects after Titration period, Fixed-Dose period,

- 623 and 4 weeks after Taper.
- 624

- 625 Taper Down: maximum duration 2 weeks
- 626 Upon completion of the Fixed-Dose period, all participants in the study will be
- 627 titrated off study drug through a taper down period of maximum 2 weeks. Taper schedule
- 628 will directly relate to maximum gabapentin dose achieved during trial and is described in
- the Table below. The study drug will be distributed in 2 separate vials representing eachof the two weeks of the Taper-Down Period. It should be noted, participants randomized
- to placebo will also receive sufficient capsules to complete a taper down. In this way, the
- 632 blind will be maintained.

AT 3600 MG	AT 2700 MG	AT 1800 MG	AT 900 MG
FOR 3 DAYS 3 MORNING 3 NOON 3 NIGHT	FOR 3 DAYS 2 MORNING 2 NOON 2 NIGHT	FOR 3 DAYS 1 MORNING 1 NOON 1 NIGHT THEN STOP	NO TAPER REQUIRED
NEXT 3 DAYS 2 MORNING 2 NOON 2 NIGHT	NEXT 3 DAYS 1 MORNING 1 NOON 1 NIGHT THEN STOP		
FINAL 3 DAYS 1 MORNING 1 NOON 1 NIGHT THEN STOP			

634 Gabapentin Taper Down Schedule

635

635	
636	End of Study Intervention: Exit Interview/ Data Collection: 4 weeks after
637	completing Taper Down
638	The RA will contact the participants to query participants about compliance
639	with taper-down schedule and maintenance of diaries. Participants will complete the
640	following forms (survey titled: "FinalSurvey"):
641	1. Clinical Global Impression of Severity Scale (CGI-S).
642	2. Clinical Global Impression of Improvement Scale (CGI-I)
643	3. University of Pennsylvania Smell Identification Test (UPSIT)
644	4. Olfactory Dysfunction Outcomes Rating (ODOR)
645	5. NASAL-7
646	6. Clinical Global Impression-Severity Scale for Parosmics (CGI-P)
647	
(10	
648	F3 Safety and Adverse Events
649	
650	3.a Safety and Compliance Monitoring
	v I O

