#### 207 *C1* **Primary** Aim

208 To evaluate the efficacy of oral gabapentin on improvement of olfactory dysfunction in 209 patients with post-COVID-19 anosmia, hyposmia, or parosmia. Participants will receive a 210 maximum of 14weeks of either gabapentin or placebo with the first four weeks serving as 211 a titration phase and the last two weeks serving as a taper-down period.

212 *C2* Secondary Aim

213 Describe the adverse effects of gabapentin. All participants will be monitored for adverse 214 effects throughout the study.

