#### 490 **3.**e **Subject Compliance Monitoring**

491 There will be check-ins with the study participants every two weeks conducted virtually 492 through the participant's preferred communication method (i.e. phone call or video call) 493 to answer questions and ensure participants are adhering to medication schedule. Subjects 494 will be asked to keep a paper calendar for daily notes of pill count, side/adverse effects,

495 and study barriers. The paper calendar will be mailed back to the RA after study 496 completion.

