### 679 **3.b Definitions of Adverse Events**

Adverse event (AE) means any untoward medical occurrence associated with the use of a
drug in humans, whether or not considered drug related (21 CFR 312.32(a)).

682

An adverse event (also referred to as an adverse experience) can be any unfavorable and
unintended sign (e.g., an abnormal laboratory finding), symptom, or disease temporarily
associated with the use of a drug, without any judgment about causality or relationship to
the drug.

687

688 An adverse event can arise from any use of the drug (e.g., off-label use, use in 689 combination with another drug) and from any route of administration, formulation, or

- 690 dose, including an overdose.
- 691

692 Serious adverse events (SAEs) are special cases of an adverse event where adverse693 outcomes are severe. SAEs include the following events:

- 694 695
- Death of any of the participants associated with a clinical trial.
- An event which can lead to life-threatening complications or put the life of participants at risk as a result of participation in a clinical trial.

698 699	•	Events that result in such a condition where the participants may require immediate hospitalization or increase the duration of hospitalization.
700	•	Any events that lead to a permanent or temporary physical disability in the body
700	•	of the participants. Any sort of incapacity is also regarded as SAE.
702 703	•	Any events that lead to any type of congenital abnormalities. It also includes any cases of birth defects resulting from the clinical trials.
704 705 706	•	Any events where an investigator or team of investigators finds feel that it can lead to significant hazards.
707 708	Class	ification of Events
709	i	Relationship
710 711 712 713 714 715 716	relation the Al (e.g., 1 AEs, 1	E or SAE may or may not be causally related to the study intervention. A causal onship means that the intervention caused (or is reasonably likely to have caused) E. This usually implies a relationship in time between the intervention and the AE the AE occurred shortly after the participant received the intervention). For all t is the responsibility of the Principal Investigator who examines and evaluates the t to determine the relatedness of the event to the study intervention.
717	ii	Severity
718 719	Sever judgm	ity refers to the intensity of a specific event and is a matter of individual clinical ent.

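### The diary instruction filters adverse effects by presumed relatedness, which contradicts the protocol's all-cause definition and may under-record mild events between contacts

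*Combined protocol and SAP*

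**What the plan says.** C2 gives the trial one secondary aim: "Describe the adverse effects of gabapentin". It adds "All participants will be monitored for adverse" effects for the whole study. Four places bear on what is written down.

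- **F2, Titration Period (diary).** Participants receive a paper calendar "and asked to maintain diaries of olfactory and taste symptoms and adverse effects", and the sentence closes by limiting these to effects "possibly related to the intervention".
- **F2, Adverse events paragraph.** The study is to capture "Any unintentional or unfavorable clinical sign or symptom, any new" illness, and any worsening of existing illness. No causal condition is attached.
- **F3 3.b.** An adverse event is defined "without any judgment about causality or relationship to" the drug. Under the Relationship heading it is the Principal Investigator's task, for all adverse events, "to determine the relatedness of the event to the study intervention".
- **E3 3.e.** Participants "will be asked to keep a paper calendar for daily notes of pill count, side/adverse effects" and study barriers. There is no relatedness condition. The calendar is mailed back after the study is complete.

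G3 specifies no adverse-event tabulation, source or comparison.

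**The concern.** A diary sheet cannot follow both F2's diary sentence and E3 3.e. Under the F2 wording, whoever makes the daily entry has to decide first whether the drug might be the cause. In a fully virtual trial (E1) that person is the participant. This puts a causality screen ahead of the record, whereas F3 3.b places it afterwards and gives it to the Principal Investigator, who cannot assess an event that was never noted.

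At stake is the completeness of the data for the only secondary aim, mainly for mild or short-lived symptoms that would not lead to a medical record or be remembered weeks later. F2 also states that the placebo is inert and not chosen to mimic gabapentin's side effects. Participants may therefore form a view of their arm, and that view could influence what they consider drug-related. If so, the loss need not be equal in the two arms.

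**Working it through.** The plan gives no adverse-event rate, so there is no figure to reproduce. The check is a comparison of texts, followed by an illustration on assumed inputs.

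**1. Scope of each text**

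| Place | What it governs | Causality condition |
|---|---|---|
| F2, diary sentence | participant's calendar | yes |
| E3 3.e | participant's calendar | none |
| F2, Adverse events | what the study captures | none |
| F3 3.b | definition of an adverse event | none; relatedness judged by the Principal Investigator |

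The two definitional texts agree with each other. The diary sentence is the outlier, and it also disagrees with the other description of the calendar.

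**2. What else could catch an event left out of the diary**

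- Staff assess adverse effects after Titration (up to 4 weeks), after the Fixed-Dose period (8 weeks) and 4 weeks after Taper (up to 2 + 4 = 6 weeks). The intervals sum to the 18-week maximum: 4 + 8 + 6 = 18.
- No forms are completed at the end of Titration; there is one call.
- FixedDoseSurvey lists an adverse-event assessment. FinalSurvey does not (F2, F4).
- The two-weekly check-ins (E3 3.e) are for questions and adherence.
- Events are abstracted from source documentation (F3 3.c), which suits events that led to care better than mild ones.

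The calendar is thus the only daily adverse-event record described. E2 2.a requires willingness to answer daily surveys, but their content is not given. The F2 flow chart was not readable in the text reviewed, so any timings shown there are unchecked.

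**3. Illustration A: equal true risk, recording depends on the participant's guess of arm**

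Let p be the true all-cause risk in both arms, gG and gP the shares of the gabapentin and placebo arms guessing gabapentin, and rG and rP the probabilities of noting an event when the guess is gabapentin or placebo. All are assumed.

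Recorded rate = p × [g × r(guess gabapentin) + (1 − g) × r(guess placebo)], so

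spurious difference = p × (gG − gP) × (rG − rP).

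- p = 0.40, guesses 0.75 and 0.35, recording 0.9 and 0.5: 32.0% against 25.6%, difference 0.40 × 0.40 × 0.40 = 6.4 points.
- Smallest non-zero case tried: 0.20 × 0.20 × 0.40 = 1.6 points.
- Largest case tried: 0.60 × 0.40 × 0.60 = 14.4 points.
- Zero if guesses are balanced or recording does not depend on the guess.

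If a share c of the missed events is recovered at the contacts, equally in both arms, each difference is multiplied by (1 − c).

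**4. Illustration B: unequal true risk, 30 per arm (60 enrolled, G1, allocated 1:1)**

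Assumed true rates are 60% and 35%: difference 25 points, SE = √(0.60 × 0.40/30 + 0.35 × 0.65/30) = 12.5 points.

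- 90% and 50% of participants noting their event: 54% − 17.5% = 36.5 points, a shift of +11.5 (0.9 SE).
- 70% in both arms: 42% − 24.5% = 17.5 points, a shift of −7.5 (0.6 SE).

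With assumed true rates of 40% and 30% (difference 10 points), the same two filters give 36% − 15% = 21 and 28% − 21% = 7 points.

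The direction is therefore not fixed. Both illustrations count the diary alone. Illustration B also applies one recording probability per participant, which overstates the loss for anyone with several events, since noting any one of them is enough.

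**The case against.** The strongest reply is that the diary is a supplementary tool and not the counting source. F3 3.c draws adverse events from source documentation and does not name the diary. The staff contacts, the FixedDoseSurvey item, the REDCap question about any adverse events (F3, Investigator only) and the exit interview for those who leave (E2 2.g) carry no relatedness filter. Participants can also reach the team at any hour. Possible relatedness is a low bar, and both arms receive similar titration and de-escalation instructions. The aim is descriptive, with no rate or test prespecified.

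Most of this stands, and it limits the point. A reader might infer that the reported adverse-event rates depend on which definition is followed and on each participant's guess of arm. The documents do not support that: no text makes the diary the source of the reported counts, and none links the blind assessment to diary entries. The role of arm guess is a plausible inference from the inert placebo and no more.

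The reply does not remove the contradiction, nor the gap between contacts. Check-ins with another stated purpose, a telephone line that relies on the participant calling, and recall over several weeks are weak substitutes for a daily note. Because the calendar comes back only after completion, staff would not see its omissions during the trial.

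**Conclusion.** The point holds as a conflict of wording with a limited consequence. F2's diary sentence contradicts the all-cause capture rule in the same section, the definition and the assignment of relatedness in F3 3.b, and E3 3.e's account of the calendar. It may cause mild or transient events between contacts to go unrecorded, possibly unequally by arm.

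The size cannot be derived from the documents. The illustrative shifts rest wholly on assumed rates and recording probabilities, assume a diary-only count that no section prescribes, and can go either way. They show that an effect is possible, not that one is expected. A claim that the between-arm comparison is biased would go beyond the text. The change is still worth making, because it costs little and protects the data for the only secondary aim.

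**What to change.** In the F2 diary instruction, delete the phrase limiting entries to effects possibly related to the intervention, and ask participants to note any new or worsened symptom or illness. Make E3 3.e and whatever instruction accompanies the calendar say the same. Leave relatedness to the Principal Investigator, as F3 3.b already provides.

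In G3, add that all-cause adverse events will be tabulated by arm, with those the Principal Investigator judged related shown separately. This is a reporting addition; G3 is silent on it now.

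The cost is one phrase in the protocol, a line in G3, and more minor entries to abstract for about 60 participants. No dose, schedule or clinical rule is affected.
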